### Overdose, Misuse

Reports of overdose and misuse, associated with the use of a Pfizer product are reported to Pfizer by the investigator, irrespective of the presence of an associated AE/SAE.

### Lack of Efficacy

Reports of lack of efficacy to a Pfizer product are reported to Pfizer by the investigator, irrespective of the presence of an associated AE/SAE or the indication for use of the Pfizer product.

#### Occupational Exposure

Reports of occupational exposure to a Pfizer product are reported to Pfizer by the investigator, irrespective of the presence of an associated AE/SAE.

### **10.1. Single Reference Safety Document**

The current Lipitor local label [package insert, (PI)] approved by China Food and Drug Administration (CFDA), will serve as the single reference safety document during the course of the study, which will be used by Pfizer safety to assess any safety events reported to Pfizer Safety by the investigator during the course of this study.

The single reference safety document (SRSD) should be used by the investigator for prescribing purposes and guidance

## **11. PLANS FOR DISSEMINATING AND COMMUNICATING STUDY RESULTS**

### **COMMUNICATION OF ISSUES**

The first publication will be the result analysis based on the primary end points of all the research units.

Investigators must inform the sponsor in advance about the publication plan of articles or reports of any study data analysis. The investigator or his/her representative must obtain review and written approval from sponsor when dealing with anything about publication or result report (magazine, abstract of newspaper or oral report, etc.), no matter in whole or in part.

The sponsor will not suppress or veto publication, but will reserve the right to delay publication for the protection of intellectual property right.

### **COMMUNICATION OF ISSUES**

In the event of any prohibition or restriction imposed (e.g., clinical hold) by an applicable Competent Authority in any area of the world, or if the investigator is aware of any new information which might influence the evaluation of the benefits and risks of a Pfizer product, Pfizer should be informed immediately.

In addition, the investigator will inform Pfizer immediately of any urgent safety measures taken by the investigator to protect the study patients against any immediate hazard, and of any serious breaches of this NI study protocol that the investigator becomes aware of.

## **13. LIST OF TABLES**

None

## **14. LIST OF FIGURES**

None

## **ANNEX 1. LIST OF STAND ALONE DOCUMENTS**

None

## **ANNEX 2. ADDITIONAL INFORMATION**

Not applicable

1 AMENDMENTS FROM PREVIOUS VERSION(S)

- Status of study when amendment (version 2) made: Study Ongoing
- Descriptions of and rationale for the changes:

Details of the Changes Rationale for the Changes

Details of the Changes	Rationale for the Changes
Week 12 is defined as Study Day 85 ± 28 days from the Day 1 study drug taken.	The LDL results at 8 weeks (2 months) from the study drug start are expected to be similar to the results at 12 weeks. Therefore in order to not unnecessarily exclude patients from the analysis, the Week 12 window has been expanded from 85 ± 10 days to 85 ± 28 days

2 INTRODUCTION

This document describes the planned data summaries and statistical analyses for Protocol A2581197, entitled “Atorvastatin Effectiveness and Safety in Cardiology patients in Real World Setting: A Registry Study in China”. It is meant to supplement the study protocol which should be referred to for details regarding the objectives and design of the study. Any deviation to this analysis plan will be described in the Clinical Study Report.

Note: in this document any text taken directly from the protocol is *italicized*.

2.1 STUDY DESIGN

Overview

This is a multi-center, prospective, observational study, which will be completed by Beijing Anzhen Hospital, Capital Medical University and approximately 64 other clinical sites.

At baseline visit, patient inclusion/exclusion and demographic information, medical history, medication records, concomitant drugs and laboratory examination results prior to atorvastatin therapy such as liver function, blood lipid parameter, creatine kinase value and renal function will be collected by investigators in the study. At week 12 visit and any unplanned visits, the laboratory examination results and medication records will be collected. Adverse events will be recorded at any time during the study period. Schedule of Activities is as follows:

Table 1: Schedule of Activities

Visits	Visit 1	Visit 2	Any unplanned visits
Protocol Activity	Baseline Day 1	Week 12 Day 85 (± 28 days)	Any Date During Week 4 to Study Close
Signed Informed Consent Form	▲		
Demographic information	▲		
Medical history	▲		
Laboratory examination	▲*	▲	▲
Inclusion/exclusion criteria	▲		
Adverse event records	Record at any time during the study period		
Medication records	▲	▲	▲

* The date of the report should be within 1 month before taking atorvastatin.

Study population

Judged by investigators, patients in cardiology department who are eligible for inclusion and exclusion criteria can be included into this study. Estimated total sample size is 10,000 and will be conducted in approximately 65 hospitals in China.

Data source

This Non-Interventional (NI) study data will be recorded in the medical records by investigators, and then input to electronic Data Collection (EDC) system as the form of electronic Case Report Form (eCRF).

Treatment/dose group

The study drug (atorvastatin) is from the doctor's prescription and will be recorded on Day 1, Week 12, and within Week 4 to end of the study. The analysis by dose groups will be taken the dose level recorded at Week 12 (Visit 2) on the prescription level or the last dose in the unplanned visit if the Week 12 is not available.

The dose groups will be in four daily dose levels, 10 mg, 20 mg, 40 mg and > 40 mg.

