#### 8.1.2. Study Endpoint

- **Primary endpoint**

- Achievement rate of LDL-C goals at 12 weeks of therapy of Atorvastatin according to Chinese Guideline on Dyslipidemia Prevention and Treatment in Adult (2007 version). It will be presented with the proportion of patients who achieve the LDL-C goal value. LDL-C target value for the patients with different risk level is defined in the [section 8.2.5](#) per guideline.

$$\text{Achievement Rate} = \frac{\text{No. subjects who achieve LDL-C target value}}{\text{No. subjects who complete 12-week follow up}}$$

- The time of 12-week will be calculated from the day when each patient starts taking atorvastatin. .
- Achievement rate will be summarized overall, within each risk strata, and by dose within each risk strata. 95% confidence intervals will be provided.

- **Secondary endpoint**

- Dosage distribution of Atorvastatin in cardiology patients with different risk stratification at the end of 12-week follow-up
- Safety and tolerability will be evaluated by recording the incidence and severity of adverse events, abnormal physical examination findings, and abnormal laboratory values through 12 weeks of treatment. Especially monitoring the patients who have any the following events:
  - Having muscle symptoms such as myalgia, fatigue, weakness, creatine kinase values 10 times the upper limit of normal, or rhabdomyolysis,
  - Having persistent elevation in alanine aminotransferase, aspartate aminotransferase, or both (defined as two consecutive measurements obtained 4 to 10 days apart that is more than three times the upper limit of the normal range).

- Major adverse cardiovascular events will also be recorded as adverse events, including death, myocardial infarction, stroke, documented unstable angina requiring re-hospitalization, revascularization with either percutaneous coronary intervention or coronary-artery bypass grafting.

Adverse events will be summarized overall and by dose within each risk strata.

- Dropout percentage and reason through 12 weeks of follow-up;

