#### Abnormal test findings

The criteria for determining whether an abnormal objective test finding should be reported as an adverse event are as follows:

- Test result is associated with accompanying symptoms, and/or
- Test result requires additional diagnostic testing or medical/surgical intervention, and/or
- Test result leads to a change in study dosing or discontinuation from the study, significant additional concomitant drug treatment, or other therapy, and/or
- Test result is considered to be an adverse event by the investigator or sponsor.

Merely repeating an abnormal test, in the absence of any of the above conditions, does not constitute an adverse event. Any abnormal test result that is determined to be an error does not require reporting as an adverse event.

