5.2 SAFETY ANALYSIS SET (SAS)

The Safety Analysis population will include all patients who receive at least one dose of study drug atorvastatin. The SAS will be the primary analysis population for all safety reporting.

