6.2 SECONDARY ENDPOINTS

- Lipid parameters (LDL-C, *High-Density Lipoprotein Cholesterol* (HDL-C), Total Cholesterol (TC), and Triglycerides (TG)) at week 12, change from baseline in lipid parameters, and %change from baseline in lipid parameters at week 12, overall, and by CVD risk group.
- *Dosage distribution of atorvastatin in patients by CV risk stratification at the end of 12-week follow-up defined as follows:*

- The atorvastatin total dose in each patient will be calculated from Day 1 to Week 12/or last dose day.
- The patient daily dose will be the total dose divided by the total days of receiving atorvastatin.
- The Week 12 dose will be the dose taken at Week 12.

- **Duration on Study**

Duration on treatment group for each subject will be calculated as last treatment day – first dose date +1

- **Adverse Events**

Any new findings or worsening of findings at post-baseline visits will be reported as adverse events.

An adverse event is considered treatment emergent relative to a given treatment if:

- the event occurs for the first time during the effective duration of treatment and was not seen prior to the start of treatment, or
- the event was seen prior to the start of treatment but increased in severity during treatment.

- **Adverse Events Special Interest (AESI)**

The Adverse Events Special Interest (AESI) will be categorized as below:

- Muscle symptoms: myalgia, fatigue, weakness, creatine kinase values 10 times the upper limit of normal, or rhabdomyolysis, and muscle damage based on significant elevated creatine kinase (CK)
- Major cardiovascular events: myocardial infarction, stroke, unstable angina requiring re-hospitalization, revascularization with either percutaneous coronary intervention or coronary-artery bypass grafting
- Death

- **Abnormal Laboratory Data**

The following elevated abnormal laboratory data will be summarized.

- Significant elevated CK: CK values 10 times the upper limit of normal,
-
-

- Persistent elevation in alanine aminotransferase, aspartate aminotransferase, or both: two consecutive measurements obtained 4 to 10 days apart that is more than three times the upper limit of the normal range
- **Dropout**
Dropout percentages and reason through 12 weeks of follow-up

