8 STATISTICAL METHODOLOGY AND STATISTICAL ANALYSES

8.1 STATISTICAL METHODS

SAS[®] Version 9.4 or later will be used to produce all listings and summary tables.

Summary tables presented by visit will include results from scheduled visits such as Day 1 and Week 12. Unscheduled visits will be listed but not summarized except in the event that an unscheduled result qualifies as a baseline result or other derived endpoint.

- **Analyses for Continuous Data**

Summary statistics for continuous variables/endpoints will be presented with number of observations (n), mean, SD, median, minimum (min), and maximum (max).

- **Analyses for Categorical Data**

Summary statistics for categorical variables/endpoints will be presented with number of observations (n) and percentages.

- **Analyses for Binary endpoints**

Exact methods (Clopper-Pearson Interval) will be used to calculate confidence interval (CI) for the primary (efficacy) endpoint: achievement rate of LDL-C at Week 12.

$$\left[\frac{r}{r + (n - r + 1)F_{1-\alpha/2;2(n-r+1),2r}}, \frac{(r + 1)F_{1-\alpha/2;2(r+1),2(n-r)}}{(n - r) + (r + 1)F_{1-\alpha/2;2(r+1),2(n-r)}} \right]$$

Where r is the proportion of patients who met therapy target level and n is the total number of patients who completed 12-weeks.

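### By-dose adverse event and dropout tables group patients by a late dose record, so events before a dose change fall under the later dose and patients with only a Day 1 record have no dose group

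*SAP*

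**What the plan says.** SAP 2.1 (Treatment/dose group) says that the prescribed dose "will be recorded on Day 1, Week 12, and within Week 4 to end of the study". It then gives the only assignment rule in either document: "The analysis by dose groups will be taken the dose level recorded at Week 12 (Visit 2) on the prescription level". A single fallback completes that sentence: "or the last dose in the unplanned visit if the Week 12 is not available". Day 1 is named as a recording point but not as a fallback. SAP 5.4 repeats the four levels (10, 20, 40 and >40 mg) and adds neither another rule nor a category for unknown dose. The average daily dose in SAP 6.2 belongs to the dosage-distribution endpoint and does not define the groups.

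The protocol asks for by-dose safety output in section 8.1.2: "Adverse events will be summarized overall and by dose within each risk strata". SAP 8.2 plans tables by dose group within risk level for adverse events, events of special interest (which include death under SAP 6.2), events leading to discontinuation, dropouts and laboratory abnormalities. Apart from the lipid analyses, these run on the safety set, defined in SAP 5.2: "The Safety Analysis population will include all patients who receive at least one dose of study drug atorvastatin". SAP 7 rules out imputation.

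**The concern.** The grouping variable is measured late, and the outcome can change it. Among the criteria in Protocol 10 for treating an abnormal test as an adverse event is this: "Test result leads to a change in study dosing or discontinuation from the study". An event may thus come before, and be the reason for, the dose under which the table later counts it.

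The rule also needs a visit after Day 1. Patients who stop, drop out or die early are the least likely to have one, and they are the patients whom the dropout and discontinuation tables exist to count.

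The background in Protocol 6 names the safety of high-intensity statin in Chinese patients as an open question, so readers will look to the by-dose tables for an answer.

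**Working it through.** **1. Apply the rule to each type of patient.**

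| Records available | Branch of SAP 2.1 | Dose group |
|---|---|---|
| Week 12 visit | first | Week 12 dose |
| No Week 12 visit, at least one unplanned visit (Week 4 onward) | second | last unplanned-visit dose |
| Day 1 only | neither | none |

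All three types are in the safety set. In the first two rows, any event before a dose change goes under the later dose. A patient lost or dead before Week 4 with no later visit is in the third row.

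**2. Laboratory tables.** By-visit Week 12 tables are largely unaffected, because value and dose come from the same visit. SAP 8.1 brings in unscheduled values where "an unscheduled result qualifies as a baseline result or other derived endpoint". Persistent ALT/AST elevation is such an endpoint, because it needs "two consecutive measurements obtained 4 to 10 days apart that is more than three times the upper limit of the normal range". With only one scheduled visit after baseline, it depends on unscheduled samples, which may precede a dose change.

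**3. Reproduce the planned figures** (SAP 2.3; Protocol 8.5). n = z²p(1−p)/d² with p = 0.60, d = 0.011 and two-sided alpha 0.05 gives 7,619.4, rounded up to 7,620, against 7,600 stated (0.3% apart). Then 7,600/(1 − 0.24) = 10,000, so planned losses are 2,400.

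**4. Patients without a dose group.** The share of losses with only a Day 1 record is not given, so the full range is shown. It is assumed that every completer has a group.

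| Share of losses with Day 1 only (assumed) | No group | Dropout % across dose columns |
|---|---|---|
| 0% | 0 | 2,400/10,000 = 24.0% |
| 25% | 600 | 1,800/9,400 = 19.1% |
| 50% | 1,200 | 1,200/8,800 = 13.6% |
| 75% | 1,800 | 600/8,200 = 7.3% |
| 100% | 2,400 | 0/7,600 = 0% |

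The overall column shows 24% in every row.

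**5. Misplaced events: illustration only.** The documents give no rate or direction of dose change. Assume 1,000 patients starting at each level, with only event patients changing dose. Shown rate = (events − moved out + moved in)/(patients − moved out + moved in).

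True risk 4% at every level, so 40 events each; 20% of event patients (8) move one level:

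| Direction | >40 mg | 40 mg | 20 mg | 10 mg |
|---|---|---|---|---|
| All down | 32/992 = 3.2% | 4.0% | 4.0% | 48/1,008 = 4.8% |
| All up | 48/1,008 = 4.8% | 4.0% | 4.0% | 32/992 = 3.2% |
| 20% down and 20% up | 4.0% | 4.0% | 4.0% | 4.0% |

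With true risks of 12%, 6%, 3% and 1.5% from >40 to 10 mg and 20% stepping down, the table shows 96/976 = 9.8%, 72/1,012 = 7.1%, 36/1,006 = 3.6% and 21/1,006 = 2.1%. The ratio of >40 to 40 mg falls from 2.0 to 1.4.

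**6. Event patients with no group: illustration only.** Take 1,000 patients with a true risk of 12% (120 events), and leave half the event patients (60) without a group.
- No non-event patients ungrouped: 60/940 = 6.4%.
- 24% of the 880 non-event patients ungrouped: 60/(60 + 668.8) = 8.2%.
- 50% of the non-event patients ungrouped: 60/(60 + 440) = 12.0%, no distortion.

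The effect on event rates depends on how much more often event patients lack a group than other patients do.

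**The case against.** The strongest reply is that little rests on these tables. SAP 4 states no hypotheses or decision rules, Protocol 8.7 keeps safety descriptive, and dose is chosen by the physician, so by-dose rates are confounded under any grouping. SAP 8.2 reports the same outcomes overall and lists dosing records with reasons for change. SAP 8.3 summarises reasons for early discontinuation for all enrolled patients, whatever their dose. The SAP's wider Week 12 window (±28 days) makes a missing Week 12 dose less common, and table shells still to come could carry an extra column. One group per patient is also simple and matches the baseline tables by dose group.

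Much of this stands, and it limits the point to the by-dose descriptive tables. It does not remove the point. A descriptive table should still put events under the dose at which they arose and account for every patient, and a listing does not change a table. Shells could add a column, but the written rule neither calls for one nor sends anyone to the Day 1 dose.

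A reader might infer that the rule makes high doses look safer than they are. The documents do not support that. The abnormal-test criterion is one of several alternatives, concerns test results only, and gives neither direction nor frequency of dose change; increases would distort the tables the other way. A reader might also infer that early deaths and dropouts vanish from the report. They do not; they can be missing only from the dose columns.

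**Conclusion.** The point holds for the by-dose tables of adverse events, events of special interest, events leading to discontinuation and dropouts, and for laboratory endpoints derived from unscheduled samples. Both faults follow from the stated rule and need no assumption about rates.

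Their size cannot be derived from the documents. For patients without a dose group, the planned loss bounds the number at 0 to 2,400 of 10,000. The upper end is a limit and not an estimate, since the 24% is a sample-size allowance for loss to follow-up and not a forecast of Day-1-only records. For misplaced events, the net direction and size are unknown: the one-directional figures show what could happen under assumed shifts and do not predict a result.

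Overall safety, overall dropout and the primary endpoint are unaffected. Correcting the rule removes misassignment, not confounding by the physician's choice of dose. The change should be made, because the protocol itself asks for adverse events by dose and the remedy needs no new data.

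**What to change.** Amend SAP 2.1 and 8.2 as follows:

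- **Adverse events, events of special interest and derived laboratory events:** tabulate by the dose being taken at onset or sampling, with person-time on that dose as denominator. Patient counts may be shown alongside. Counts of patients ever exposed are not enough as the sole denominator, because time on each dose differs.
- **Dropouts and events leading to discontinuation:** tabulate by the last dose taken, falling back to the Day 1 dose if there is no later record.
- **All by-dose safety and dropout tables:** add a category for dose not available, so that the dose columns reconcile with the overall column.
- **Unchanged:** keep the Week 12 dose for the dosage-distribution endpoint and for by-visit Week 12 tables.

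Protocol 8.3 already collects dose, duration and dose changes with reasons, and SAP 6.2 already derives total dose from Day 1, so no new data are needed. The cost is SAP wording and some derivation programming. The downside is that a patient can contribute to more than one dose group in the adverse event tables, which a footnote should state. An event that appears only some time after a dose change may still sit under the wrong dose.

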effectiveness and safety data in Chinese population, especially large-scale study in real world setting. Therefore, the study is to verify atorvastatin effectiveness and safety in Chinese population, and explore the optimal atorvastatin regimens in high-to-moderate risk for ASCVD.

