8.2 STATISTICAL ANALYSES

- **Analysis of Primary (Efficacy) Endpoint**

The primary (efficacy) analysis will be conducted in the FAS analysis population. The proportion of Achievement rate for LDL-C at Week 12 defined as the primary endpoint will be analyzed by calculating a point estimate with confidence interval (CI).

Achievement rate for LDL-C will be summarized overall, within each CVD risk strata, and by dose group within each CVD risk strata. 95% confidence intervals will be estimated.

In addition, percentage of patients who achieve LDL-C therapy target will also be tabulated by sex, age group, dose group and baseline disease type.

- **Secondary Endpoints and Safety Analyses**

Analysis of lipid values and change and percent change in lipid values at week 12 will be performed on the FAS populations. Analysis of the remaining secondary endpoints and safety data will be done on SAS (See [Section 5.2](#)). Data summaries will be presented in tabular and/or and summarized descriptively, where appropriate.

Lipid Parameters

Descriptive summary will be tabulated overall and by dose group within each CVD risk level for percent (%) change from baseline for TC, HDL-C and LDL-C and TG at Week 12.

Study Drug Exposure

Exposure to atorvastatin will be summarized descriptively overall, and by CVD risk level. Duration (days) of study drug taken, daily dose, dose at week 12, and total dose will be summarized. Listings of dosing records with the reason of change dose will also be provided.

Adverse Events

Adverse events will be classified using the medical dictionary for regulatory activities (MedDRA) classification system. The severity of adverse events will be graded according to the principal investigatory judgment and collected in CRF.

Adverse events (such as treatment emergent adverse events; treatment-related adverse events; and serious adverse events, adverse event from early termination to final visit, will be summarized by system organ class (SOC) and preferred term (PT) according to MedDRA terminology.

Adverse events will be summarized overall and by dose group within each CVD risk strata by SOC and preferred term.

Adverse events of special interest ([section 6.2](#)) will be tabulated by preferred term (PT) overall and by dose group within each CVD risk level.

Adverse events leading to discontinuation of trial treatment will be presented overall and by dose group within each CDV risk level.

Dropouts

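### The dose used to group LDL-C goal rates is not required to precede the LDL-C sample, so the result can decide which dose group a patient is counted in

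*SAP*

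**What the plan says.** SAP 2.1 (Treatment/dose group) sets the rule: "The analysis by dose groups will be taken the dose level recorded at Week 12 (Visit 2) on the prescription level". A fallback covers patients without that record: "or the last dose in the unplanned visit if the Week 12 is not available". The section also fixes the categories: "The dose groups will be in four daily dose levels, 10 mg, 20 mg, 40 mg and > 40 mg".

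These groups are applied to the primary endpoint. Protocol 8.1.2 lists the summary under that endpoint: "Achievement rate will be summarized overall, within each risk strata, and by dose within each risk strata". SAP 8.2 repeats it: "Achievement rate for LDL-C will be summarized overall, within each CVD risk strata, and by dose group within each CVD risk strata", with 95% confidence intervals. SAP 8.2 also tabulates percent change in lipids by dose group within risk level.

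SAP 6.2, under dosage distribution, words the Week 12 dose differently: "The Week 12 dose will be the dose taken at Week 12".

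Four other provisions matter here:
- Laboratory results and medication records are collected at the same Week 12 visit and at any unplanned visit (Protocol 8.2.7, SAP 2.1).
- SAP Table 1 lets unplanned visits run to study close.
- Dosing follows the doctor's prescription (Protocol 8.2.8).
- Dose, duration, and dose changes with their reasons are recorded (Protocol 8.3).

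**The concern.** A goal rate by dose is readable only if the dose was being taken before LDL-C was measured. The rule in SAP 2.1 does not secure that order. A patient may take 20 mg up to the sample, miss goal, and be recorded at that visit with a prescription for 40 mg. Read literally, the rule allows this patient to be counted as a 40 mg failure. The 20 mg group loses a failure and the 40 mg group gains one that its dose did not produce.

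The fallback has the same weakness. The last unplanned-visit dose may have been set on or after the date of the LDL-C sample.

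What is at stake is the by-dose split of the primary endpoint and the by-dose lipid changes. Protocol 6 says the study is meant to "explore the optimal atorvastatin regimens in high-to-moderate risk for ASCVD", and the same section discusses whether moderate doses are enough in Chinese patients. Readers will look to these tables for that. If non-achievers are moved up, the tables will understate, and could reverse, any advantage of the higher dose.

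**Working it through.** **The plan's own figure.** The only planned precision is for the overall rate (Protocol 8.5, SAP 2.3): 60% achievement, allowable error 1.1 points, type I error 0.05, taken as two-sided.
- n = 1.96² × 0.6 × 0.4 / 0.011² ≈ 7,619, against 7,600 stated.
- 7,600 / (1 − 0.24) = 10,000, as stated.

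Both reproduce and neither is disputed. The documents give no figure for the by-dose results.

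**Model.** There are two doses. Of 100 patients, N_L take the lower and N_H the higher dose up to the Week 12 sample, with true goal rates p_L and p_H. A share f of the lower-dose non-achievers is recorded at that visit with the higher dose.
- Patients moved: m = f × N_L × (1 − p_L)
- Reported lower-dose rate: N_L p_L / (N_L − m)
- Reported higher-dose rate: N_H p_H / (N_H + m)

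The dose mix, the true rates and f are all assumptions; none is in the documents.

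**Case A: 80/20 split, true rates 60% and 70%.** There are 48 lower-dose achievers, 32 lower-dose non-achievers and 14 higher-dose achievers.

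| f | m | Lower dose | Higher dose | Higher minus lower |
|---|---|---|---|---|
| 0 | 0 | 48/80 = 60.0% | 14/20 = 70.0% | +10.0 |
| 5% | 1.6 | 48/78.4 = 61.2% | 14/21.6 = 64.8% | +3.6 |
| 10% | 3.2 | 48/76.8 = 62.5% | 14/23.2 = 60.3% | −2.2 |
| 20% | 6.4 | 48/73.6 = 65.2% | 14/26.4 = 53.0% | −12.2 |

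Reversal: 48(20 + m) = 14(80 − m) gives 62m = 160, so m = 2.58 and f = 2.58/32 = 8.1%.

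**Case B: 50/50 split, true rates 55% and 65%.** There are 27.5 lower-dose achievers, 22.5 lower-dose non-achievers and 32.5 higher-dose achievers.
- f = 10%: m = 2.25; 27.5/47.75 = 57.6% vs 32.5/52.25 = 62.2% (+4.6 points).
- f = 20%: m = 4.5; 27.5/45.5 = 60.4% vs 32.5/54.5 = 59.6% (−0.8 points).
- Reversal: 27.5(50 + m) = 32.5(50 − m) gives 60m = 250, so m = 4.17 and f = 4.17/22.5 = 18.5%.

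**What does not change.** The overall rate is (48 + 14)/100 = 62% in case A and (27.5 + 32.5)/100 = 60% in case B, for every f. Rates by risk stratum are equally untouched, because moving a patient between dose groups does not change the stratum. If the grouping dose is the one in force before the sample, m = 0 and the +10 points stand.

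**Would sampling error hide it?** In case B with 7,600 patients pooled over strata, the by-dose 95% half-widths are about 1.4 to 1.7 points. Within strata they would be wider. A shift of 5 to 10 points in the difference would still look precise in the pooled table.

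**The case against.** The strongest reply is that SAP 2.1 may simply mean the prescription in force when the patient arrives. Protocol 8.3 describes medication records as dosage, duration and changes, which fits treatment already taken. SAP 6.2 speaks of a dose taken. No section says that a new prescription is issued at Visit 2, or that the LDL-C result is known when the dose is decided. This stands in part: a reader might infer that the SAP necessarily uses the post-result prescription, and the text does not establish that. It does not exclude it either. The SAP 6.2 wording belongs to dosage distribution, while SAP 2.1 governs the dose-group analysis.

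Three other stronger readings also lack support.
- **Same direction of bias in every risk stratum.** The direction shown holds when non-achievers are moved up. A non-achiever moved down, for example for tolerability, would push the contrast the other way. The documents give no direction or frequency of dose changes for any stratum.
- **Any change at an unplanned visit is too recent for the LDL-C result to reflect the new dose.** The protocol's unplanned-visit window starts at Day 29 with a 10-day tolerance, and the SAP accepts samples up to Day 113 (85 + 28), so the interval can be long. The SAP's remark, "The LDL results at 8 weeks (2 months) from the study drug start are expected to be similar to the results at 12 weeks", concerns time from drug start and sets no interval after a dose change.
- **Regimen choice is a study objective.** It appears in the background only, not in Protocol 7 or SAP 2.2.

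It is also fair to say that the analysis is descriptive (SAP 4.1, 5.4, 6.4) and that confounding by indication would affect by-dose rates under any grouping. Both are true. Neither justifies assigning a result to a dose started after it, which is a separate and avoidable error.

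**Conclusion.** The concern holds as a defect in the definition. SAP 2.1 and 6.2 describe the Week 12 dose in two unreconciled ways, and the one governing the by-dose analysis allows the outcome to determine the group. The effect is confined to by-dose goal rates and lipid changes for the points made here; the overall primary result and the risk-stratum rates are safe.

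The size cannot be stated from the documents. Under the assumed mixes, a true 10-point advantage for the higher dose disappears when about 8% (case A) or 18.5% (case B) of lower-dose non-achievers are recorded at the higher dose after the sample. It shrinks without reversing below those shares, and is unchanged if the dose in force is used. The rule should be settled before the by-dose tables are produced.

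**What to change.** 1. In SAP 2.1 and 8.2, define the dose group for LDL-C achievement and lipid change as the daily dose in use immediately before the LDL-C sample, excluding any change made on or after the sample date.
2. Apply the same date rule to the unplanned-visit fallback.
3. Align SAP 2.1 with SAP 6.2 so that one definition of the Week 12 dose is used.
4. Add a supportive table by Day 1 prescribed dose, because titration for response before the sample would remain under item 1. This table has its own limit: Protocol 8.2.3 excludes only regular atorvastatin use beyond 4 weeks, so for some patients the Day 1 dose may already reflect earlier treatment.
5. State with the by-dose tables that the rates are descriptive and subject to titration and confounding by indication.

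The cost is a few sentences in the SAP and one extra set of tables. The dose, duration and dose-change data are already collected under Protocol 8.3, and no clinical procedure changes.
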